### **7.3 Data Analysis**

Improvements in subject quality of life after surgery will be assessed by constructing 95% confidence interval for the mean change from baseline score in EQ-5D-5L and FAMM total and component scores.

|   |  |  |
|---|--|--|
|  | Clinical Investigation Plan
Foot and Ankle Products | CIP- INT19-MDR-001
Version: 2 |
|---|--|--|

Survivorship of a Wright product will be assessed based on adverse event resulting from the presence or performance of the device. The Kaplan Meier survivorship method and life table analysis will be employed. Time to adverse event due to the presence or performance of the implant will be the survivorship endpoint for each Wright device. Also, time to reoperation to exchange or remove any part of the Wright device due to failure of the implant will also determine the Wright product survivorship. Subjects who will not experience these events will be censored at the last follow-up visit. The Kaplan Meier survival curve and the 95% Confidence Interval will be constructed.

Safety endpoints will include all adverse events (AE), serious AE (SAE), unanticipated adverse device effects (UADEs).

All subjects enrolled in the study will be assessed for safety. Adverse events and other safety evaluations will be reported as frequency and rates as appropriate, cumulative over the different follow-up schedules.

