**6.2.2 Criteria and Procedures for Subject Withdrawal or Discontinuation**

Subjects maintain the right to discontinue their participation in the study at any point without penalty or loss of benefit to which the subject is otherwise entitled per ICH E6 4.8.10(m) guidelines. If at any time the study device is removed, the subject will be discontinued from the study unless the subject has other study devices remaining.

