## **7.0 Statistical Considerations**

### **7.1 Study design**

This study is a global, multi-center, post-market observational study to demonstrate the safety and performance of the Wright products listed in Section 3.3. Data will be collected at baseline, surgery, at the last scheduled standard of care and/or surgeon release follow-up (FU) time point. The subjects improvement in post-surgical quality of life will be assessed using EQ-5D-5L and Foot and Ankle Ability Measure (FAAM).

An adverse event resulting from the presence or performance of the device and removal due to implant failure will determine the survivorship of the Wright product. Further, safety will be assessed by subject experience of device complication and adverse events during the study period.

All effectiveness and safety analysis will be performed separately for each Wright Medical device included in the study.

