##### **11.4.2 Sponsor Reporting**

**Recording and Reporting Adverse Events - Wright Medical Responsibilities**  
Wright Medical is responsible for the classification of AEs and ongoing safety evaluation of the study and will:

- Review the Investigator's assessment of all AEs; determine and document, in writing, the seriousness of the adverse event and relationship of the adverse event to the implanted components.

In case of a disagreement between Wright Medical and the Investigator, Wright Medical shall:

- Communicate both opinions to concerned parties; and
- As required, ensure that the IRB/EC/REC and regulatory authorities are informed of significant new information involving the product during the study
- Or seek independent review as needed.

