## 8.2. Appendix 2 – Listing of Tables and Listings, Table Templates

### A. LISTING OF TABLES

Table	1.1	Subject Accounting
Table	1.2	Subject Eligibility
Table	1.3	Demographics and Clinical Characteristics
Table	1.4	All Protocol Deviations
Table	1.5	Medical History
Table	2.1	Surgical and Operative Information
Table	2.2	Additional Surgical Procedures Performed
Table	3.1	EQ-5D by device and visit
Table	3.2.1	FAAM score by device and visit
Table	3.2.2	FAAM overall rating by Device and Visit
Table	4.1	Surgeon assessment by device
Table	4.2	Radiographic assessment by device
Table	5.1	Life table for time to first device related adverse event by device
Table	5.2	Life table for device failure by device
Table	5.3	Life table for time to death by device
Table	6.1	Adverse event by device

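### Both device-survivorship endpoints depend on causal attribution, and no planned table shows how often a device was removed for any reason

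*Protocol*

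**What the plan says.** Protocol 7.1 and 7.3 give two survivorship events. The first: "Time to adverse event due to the presence or performance of the implant will be the survivorship endpoint for each Wright device". The second is "time to reoperation to exchange or remove any part of the Wright device due to failure of the implant", and 7.1 carries the same restriction: "removal due to implant failure will determine the survivorship of the Wright product". For everyone else, "Subjects who will not experience these events will be censored at the last follow-up visit". Protocol 6.2.2 adds: "If at any time the study device is removed, the subject will be discontinued from the study unless the subject has other study devices remaining".

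SAP 6.6 (Harms and Safety) takes device failure as the basis of the survival rates. SAP Appendix 2A lists three life tables: 5.1 for first device-related adverse event, 5.2 ("Life table for device failure by device") and 5.3 for death. The template section reuses the number 5.1 for the adverse event summary; below, Tables 5.1 and 5.2 mean the life tables.

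On attribution, the site records the relationship to device and procedure (Protocol 11.2, 11.3). The sponsor reviews that assessment and must "determine and document, in writing, the seriousness of the adverse event and relationship of the adverse event to the implanted components" (11.4.2). If the two disagree, both opinions are communicated, or independent review is sought as needed. The synopsis lists no committee. Neither document defines implant failure or device failure, or says who decides it.

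**The concern.** A device can leave the body for reasons that nobody attributes to the device or to its failure. Such a removal is not an event in either curve. Where it ends the subject's participation, the analysis treats it like an intact implant that was no longer followed. Where the subject keeps another study device, the subject stays in the study and the censoring rule refers to the subject's last visit, so the removed device can go on counting as surviving.

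The study exists to give regulators and notified bodies evidence on safety and performance for each device. How often the implant was still in place is a basic question for that reader. No planned table answers it, and the tables that come closest depend on an undefined classification. Devices are summarised from 10 implanted patients upward (SAP 3.1), so the classification of a single removal can move a device's figure by about 10 points.

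**Working it through.** **The plan's own figure.** The documents state no survival, failure or removal rate, so there is none to reproduce. The only derived figure, the sample size per device, reproduces: (1.96 × 0.313 / 0.1)² = 37.63, rounded up to 38. It has no bearing on this point.

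**What happens to each kind of removal**

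| Removal | Treatment under the plan |
|---|---|
| Follows a device-related adverse event | Event in Table 5.1 |
| Attributed to implant failure | Event in Table 5.2 |
| Neither, no other study device | Discontinued (6.2.2), censored at last visit (7.3) |
| Neither, another study device remains | Stays in study; removed device can remain at risk until last visit |

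**Direction.** Take failure as the reoperation event of Protocol 7.3. Any-reason removals then include all failure events. With the same risk sets, each Kaplan-Meier factor for any-reason removal is at or below the factor for failure alone. Failure survivorship is therefore never lower. This ordering does not extend to Table 5.1, which also counts device-related events that lead to no removal.

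**Size, with assumed counts.** Take 20 patients, k non-failure removals, then one failure removal, and everyone else followed to the end.

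- Failure only, others censored: 1 − 1/(20 − k)
- Any reason: 1 − (1 + k)/20

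| k | Failure only | Any reason | Gap (points) |
|---|---|---|---|
| 0 | 95.0% | 95.0% | 0 |
| 1 | 18/19 = 94.7% | 90.0% | 4.7 |
| 2 | 17/18 = 94.4% | 85.0% | 9.4 |
| 4 | 15/16 = 93.8% | 75.0% | 18.8 |

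**Other device sizes, also assumed**

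- n = 10, one failure at month 6, other removals at months 4 and 9: 8/9 = 0.889 against 7/10 = 0.700.
- n = 40, failures at months 4 and 8, other removals at months 3, 5, 7 and 10: (38/39) × (35/36) = 0.947 against 34/40 = 0.850.

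**Range.** With constant hazards over one year, failure survival is 1 − f and any-removal survival is (1 − f)(1 − r), where f is the failure risk and r the other-removal risk. For f = 5% and r = 10%: 0.950 against 0.95 × 0.90 = 0.855. Over f of 2–10% and r of 0–20%, the gap runs from 0 to 0.196.

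**Removed device left at risk.** n = 10, one non-failure removal at month 4, one failure at month 6. Censored at removal: 1 − 1/9 = 0.889. Kept at risk because another study device remains: 1 − 1/10 = 0.900.

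**The case against.** The strongest reply is that failure-specific survivorship answers a sound question about device performance. The product list includes external fixation (Protocol 3.3), where removal in the ordinary course is not a loss of survival, so an any-reason curve alone would mislead. A cause-specific curve is also meant not to move with other causes, and its stability in the example is no evidence of bias. All of this stands, and it is why the any-reason table should be supplementary.

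Four stronger readings are tempting, and the documents do not support them.

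- *Only failure removals count.* Protocol 7.3 makes device-related adverse events a survivorship endpoint in their own right, with Table 5.1. An event caused by the mere presence of the device qualifies, so many removals may be captured there. In the example with f = 5% and r = 10%, counting half of the other-removal hazard as device-related events alongside failures gives 0.95 × √0.90 = 0.901, roughly halving the gap to 0.855. Table 5.2 itself would still show 0.950.
- *The sponsor decides what is a failure.* Protocol 11.4.2 gives the sponsor the seriousness and relationship of adverse events, after the investigator's own assessment. It does not mention implant failure. The gap is that nobody is named.
- *Other removals disappear.* They may appear in the surgery row of the adverse event template, in Listings 9 and 10, or in the yearly Patient Survey. But the surgery row covers only treatment of adverse events and does not separate removal, and the discontinuation reasons in the Table 1.1 template have no removal category. Table 2.2, on additional surgical procedures, is listed with the operative tables and is not a time-to-event display.
- *The study's main safety result is distorted.* The primary endpoint is EQ-5D, all analyses are descriptive, and survivorship is one of several safety displays.

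**Conclusion.** The point holds in limited form. Both survivorship endpoints need an attribution, failure is undefined, no adjudicator is named, and no planned table gives removals for any reason. Failure survivorship can then only equal or exceed any-removal survivorship. For subjects with several study devices, the censoring rule as written can also leave a removed device in the risk set.

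The size is unknown. The 94.4% against 85.0% rests on assumed counts and compares two different quantities; it is not an estimate of bias. The gap is zero if every removal is attributed to failure. The ordering also assumes that the SAP's device failure means the reoperation event of Protocol 7.3; if it includes failed devices left in place, the ordering is not guaranteed. This is a cheap improvement in reporting, and the planned curves remain valid for the question they ask.

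**What to change.** Keep Tables 5.1 and 5.2 as planned, and make three changes to the SAP.

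1. In the failure analysis, end each device's at-risk time at its own removal, whether or not the subject keeps another study device.
2. Add one supplementary table per device: first removal, exchange or reoperation for any reason, with counts by recorded reason so that planned or elective removals, such as those of external fixation, are visible.
3. State which recorded item makes an event a device failure and whose entry counts.

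Dates and reasons should come from the adverse event form and the Surgical Intervention records. The form as described in Protocol 11.3 has onset and resolution dates but no separate removal date, and the contents of the Surgical Intervention record are not described. The yearly Patient Survey asks about removal with no stated date or reason, so where it is the only source, show a count by visit interval.

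The cost is SAP wording and one extra table. The any-reason figure will be no more favourable than the failure figure and will include elective removals, so it should be labelled supplementary and shown with the reasons beside it.

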### 3. Statistical Procedure

#### 3.1. FRAMEWORK

The purpose of this statistical analysis plan is to guide the analysis and production of statistical output for the Wright Foot & Ankle Post-Market Observational Study. The company decided to discontinue enrollment to the study on November 1, 2021. At study end date, there were 122 patients enrolled in the study. The sample size of 40 patients per device that was originally planned in the study was therefore not met.

The study required at least 40 sample size for each Wright medical device (See INT19-MDR-001 Protocol, Version 3). For the same sample size parameters in the protocol  $n=10$ , will yield a power of 0.5. Thus, for the purpose of reporting statistically valid outcomes, descriptive summary statistics will be presented for Wright devices implanted in at least 10 patients enrolled in the study. Patient data on devices that has less than 10 implanted patients will be provided in the listings to be made available for future study or reference. Appendix Table 1 lists the Wright devices that are included in the study.

As the goal of the study is to determine the performance and safety of each device under investigation, analysis of outcomes will be done for each device the patient received. Note that a patient may have received more than one of the Wright devices. In all analysis of outcomes, patient level data will be included in the analysis for each device he/she received.

All analysis to be conducted are of descriptive nature only. No test of hypothesis will be performed. All quantitative variables, including those based on calculations (i.e., improvement from baseline), will be analyzed with a case summary evaluation before the detailed characteristics and parameter can be evaluated. A case summary contains a listing of the number of valid cases/values, missing cases/values (if any) and total cases/values in the specific analysis. The mean and median will be reported to assess the average or centrality of quantitative variables. Improvement from baseline in patient reported outcome (PROM) will be assessed at each post-surgery visit. Improvement will be based on the difference in raw scores.

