Whenever the available data allows, the standard deviation, interquartile range (IQR) and maximum and minimum will be calculated. All quantitative variables will be assessed for normality via the Shapiro-Wilk test. The 95% confidence interval (CI) of the mean will be presented when the normality of the data is met.

All qualitative variables, including those based on summaries (secondary elements), will be analyzed listing the proportions, frequencies, column and row totals and missing proportion (if any).

The proportion of device surviving at each visit will be summarized for each device. Rates will be computed based on available data. Missing data will not be imputed.

No imputations for missing data will be conducted.

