## 8. Appendices

### 8.1. Appendix 1. List of Wright medical devices included in the study.

Device	Follow-Up Time Period
611 Nail	1 year
BIOARCH	1 year, 2 year
BIOFOAM Ankle Spacers	1 year
BIOFOAM Wedge System	1 year
CHARLOTTE MUC Screws	1 year
CHARLOTTE Quick Staple	1 year
CHARLOTTE Snap-Off Screws	1 year
CLAW II	1 year
DARCO Headed Screws	1 year
DARCO Headless Screws	1 year
DARCO MFS	1 year
DARCO MRS	1 year
DARCO Plantar Lapidus Plate	1 year
DART-FIRE	1 year
FUSEFORCE	1 year
FUTURA CSI	1 year, 2 year
G-FORCE	1 year, 2 year
GRAVITY SYNCHFIX	1 year, 2 year
HV Screws	1 year
MaxLock Edgelock Plate	1 year
MiniMaxLock ISO Plate	1 year
MICA Screws	1 year
NEXFIX Snap-Off Screws	1 year
Omni Evolution Screws	1 year
ORTHOLOC 2 Ankle Fracture	1 year
ORTHOLOC 2 CROSSCHECK	1 year
ORTHOLOC 2 Small Bones	1 year
ORTHOLOC 3Di Ankle Fusion	1 year
ORTHOLOC 3Di Hallux	1 year
ORTHOLOC 3Di Midfoot/Flatfoot	1 year
ORTHOLOC Forefoot Fracture	1 year
ORTHOLOC Plantar Lapidus	1 year
ORTHOLOC Calc Fracture	1 year
PHALINX	1 year
PITON	1 year
PRO-TOE VO	1 year
SALVATION ExFix	1 year
SALVATION Bolts and Beams	1 year
SALVATION 3Di Plates	1 year
SWANSON Toes	1 year, 2 year, 3 year, 4 year, 5 year, 6 year, 7 year, 8 year, 9 year, 10 year
Telya	1 year
UNIMA EVO and NEUTRA Screws	1 year
VALOR Nail	1 year

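### Survivorship time follows the subject rather than the device, so a device removed without a survivorship event can stay in its own risk set after it is out

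*Protocol*

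**What the plan says.** Protocol 7.3 names two survivorship endpoints. The first: "Time to adverse event due to the presence or performance of the implant will be the survivorship endpoint for each Wright device". The second is "time to reoperation to exchange or remove any part of the Wright device due to failure of the implant". Protocol 7.1 limits removal in the same way: "removal due to implant failure will determine the survivorship of the Wright product". The only censoring rule in either document is in Protocol 7.3: "Subjects who will not experience these events will be censored at the last follow-up visit".

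Protocol 6.2.2 says that when a study device is removed, "the subject will be discontinued from the study unless the subject has other study devices remaining".

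Protocol 7.1 asks for separate analyses for each device. SAP 3.1 says "Note that a patient may have received more than one of the Wright devices" and puts such a patient's data into the analysis of every device received.

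On survival, SAP 3.1 adds "The proportion of device surviving at each visit will be summarized for each device. Rates will be computed based on available data". SAP 6.6 bases survival rates on device failure. SAP Appendix 2A lists separate life tables for first device-related adverse event and for device failure. The SAP gives no censoring rule and says nothing about removal without failure.

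**The concern.** The estimate is per device, but the clock that stops it is the subject's. Suppose a device is taken out for a reason that is not a survivorship event. If it was the subject's only study device, the subject leaves and the device stops contributing. If another study device remains, the subject keeps attending, and under the stated rule the absent device goes on counting as event-free until that subject's last visit. Exposure after the same removal then depends on what else was implanted.

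The study is meant to show notified bodies that each product is safe and performs as intended. Time with no device in place cannot yield a failure of that device, so including it lowers the apparent failure rate relative to devices actually in place.

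**Working it through.** **The passages together.**

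- A removal caused by implant failure is an event, so there is no problem.
- A removal accompanied by a device-related adverse event, but not caused by implant failure, is an event on the adverse-event curve. It is not one on the device-failure curve.
- A removal with neither is not an event on either curve.
- In the last two cases, on the curve where no event is recorded, the censoring date is the subject's last visit. By Protocol 6.2.2 this falls after removal if another study device remains, and about at removal if none does.

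**The plan's own figures.** The documents give no survivorship figure to reproduce. The sample size comes from EQ-5D precision: (1.96 × 0.313 / 0.1)² = 37.63, rounded up to 38 as stated, with a minimum of 40 per device. I take 40 only as a convenient illustrative size; SAP 3.1 says that target was not met.

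**Illustration (all rates assumed).** N devices; r removed at month 3 without a survivorship event; f failures at month 9 among the rest; all other follow-up to month 12. Let s of the r removals be in single-device subjects, whose last visit falls before month 9. One-year failure is then:

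- as written: f / (N − s), because only single-device removals leave the risk set;
- censored at removal: f / (N − r);
- cumulative incidence with removal as a competing event: ((N − r)/N) × (f/(N − r)) = f / N.

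With N = 40, f = 2 and all removals in multi-device subjects (s = 0):

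| r | As written | Censored at removal | Competing event |
|---|---|---|---|
| 0 | 2/40 = 5.00% | 2/40 = 5.00% | 5.00% |
| 4 | 5.00% | 2/36 = 5.56% | 5.00% |
| 8 | 5.00% | 2/32 = 6.25% | 5.00% |
| 12 | 5.00% | 2/28 = 7.14% | 5.00% |
| 20 | 5.00% | 2/20 = 10.00% | 5.00% |

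Device-years at r = 8: as written, 38 × 1 + 2 × 0.75 = 39.5. Censored at removal, 30 × 1 + 2 × 0.75 + 8 × 0.25 = 33.5.

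**Effect of the mixture.** Hold r = 20 and vary s. As written, failure is 2/40 = 5.00% at s = 0, 2/30 = 6.67% at s = 10 and 2/20 = 10.00% at s = 20. Removals and failures are identical in all three. Only the share of subjects with another device changes, and at s = 10 the result matches neither of the other two estimates.

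**At the SAP's reporting threshold.** With N = 10, f = 1, r = 2 and s = 0, failure is 1/10 = 10.0% as written and 1/8 = 12.5% with censoring at removal.

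**The case against.** **The written rule may give the right answer to a different question.** With complete follow-up and every removal in a multi-device subject, the as-written 5% is the proportion of implanted devices that fail by one year, that is, the competing-event cumulative incidence. Censoring at removal instead estimates failure had devices stayed in, and assumes removal is unrelated to failure risk. This stands, and it means any claim of bias must name its target. It does not rescue the rule, because single-device removals are in effect censored at removal, so the curve is in general a blend of the two.

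**Last follow-up could be read per device.** Analyses are per device, and follow-up length is set by product (Protocol 6.1.2 footnote 4 and 6.3.5.3; SAP Appendix 1). The reading is open, but the censoring sentence speaks of subjects, and the product schedules run to a clinical-lifetime requirement, not to removal. Even on this reading, no text stops the clock when a device comes out.

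**A reader might infer that the SAP counts a removed device as surviving.** It does not say so. It sets no denominator rule at all; the gap is silence.

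**A reader might infer a several-fold understatement of failure.** With 30 of 40 devices removed, the formulas give 2/10 = 20% against 5%. That needs three quarters of devices out by month 3, all without a survivorship event and all in multi-device subjects, with both failures among the remaining 10, and it holds only against survival while in place. Nothing in the documents supports such rates.

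**A reader might single out the external fixator**, listed as "SALVATION ExFix 1 year". That a frame comes off within the year, in a subject who also has internal study hardware, is an assumption; the documents state neither.

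**Survivorship is not the primary endpoint**, and the SAP is descriptive with no hypothesis tests. This limits the weight of the point.

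**Conclusion.** The point holds as a defect in how time at risk is defined. Followed literally, Protocol 7.3 with 6.2.2 treats one event in two ways according to whether another study device is present, so the per-device curve is in general neither survival while in place nor cumulative incidence. Relative to survival while in place, survival is never understated; it is too high whenever failures follow such removals. If none follow, the point estimate is unchanged and only the numbers at risk are wrong.

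The size is unknown. The 5% against 5.6% to 10% comparison rests on assumed removals, failures and timing. The issue is confined to multi-device subjects. A removal with a device-related adverse event affects only the device-failure curve. It should be corrected before the life tables are produced, but it does not touch the EQ-5D analysis.

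**What to change.** In Protocol 7.3 and SAP 3.1 and 6.6, and for the life tables of first device-related adverse event and of device failure:

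- Define time at risk per device, ending at the earliest of the event for that curve, removal of that device, and the last follow-up visit, whether or not the subject stays in the study. Protocol 6.2.2 need not change.
- Leave removed devices out of later denominators for the proportion surviving at each visit.
- Add a companion line that counts removal for any reason as an event, or report removal as a competing event. In the illustration with r = 8, removal or failure by one year is (8 + 2)/40 = 25%, which the failure curve alone does not show.
- Name the life tables by title, because the SAP attaches the number 5.1 both to a life table and to the adverse-event table.

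The programming is minor, but the data need checking. Protocol 6.3.5.3 lists device removal on the yearly patient survey. Protocol 11.3 lists event dates but no removal date per device. The content of the surgical-intervention record in Protocol 6.1.2 is not described. The sponsor should confirm that one of these gives the date and reason of removal for each device.

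Fewer devices will be at risk late, so intervals widen somewhat. If every device of a type is out before a visit, nobody is at risk then and survival while in place cannot be observed at that time; the table should say so.
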